#### **8.1.5.2 Concomitant Medications**

The investigator or qualified designee will record medication and non-study vaccination on the appropriate eCRF, if any, taken by the participant during the study per data entry guidelines.

If a medical condition requires the use of a prohibited steroid regimen, immunoglobulin, blood, or blood products during a participant's participation in this study, one of the individuals listed on the Sponsor Contact Information page must be notified as soon as possible.

### **8.1.6 Assignment of Screening Number**

All consented participants will be given a unique screening number that will be used to identify the participant for all procedures that occur prior to intervention allocation. Each participant will be assigned only 1 screening number. Screening numbers must not be re-used for different participants.

Any participant who is screened multiple times will retain the original screening number assigned at the initial screening visit. Specific details on the screening/rescreening visit requirements are provided in Section 8.12.1.

### **8.1.7 Assignment of Treatment/Allocation Number**

All eligible participants will be allocated, by nonrandom assignment, and will receive a treatment/allocation number. The treatment/allocation number identifies the participant for all procedures occurring after treatment allocation. Once a treatment/allocation number is assigned to a participant, it can never be re-assigned to another participant.

A single participant cannot be assigned more than 1 treatment/allocation number.

### **8.1.8 Study Intervention Administration**

Study vaccines should be prepared and administered by appropriately qualified members of the study personnel (eg, physician, nurse, physician's assistant, nurse practitioner, pharmacist, or medical assistant) as allowed by local/state, country, and institutional guidance.

Study intervention is given on the day of treatment allocation/randomization or as close as possible to the date on which the participant is allocated/assigned.

#### **8.1.8.1 Timing of Dose Administration**

Study vaccine will be administered as indicated in Section 1.3. All participants will be monitored for any immediate reactions as per local standard of care.

Participants must be afebrile for at least 72 hours prior to vaccination (Section 1.3).

Blood samples must be collected before study vaccination on Day 1.

### **8.1.9 Discontinuation and Withdrawal**

Participants who receive a single-dose intervention cannot discontinue study intervention (see Section 7.1).

Participants who withdraw from the study should be encouraged to complete all applicable activities scheduled for the final study visit (Visit 2) at the time of withdrawal. Any AEs that are present at the time of withdrawal should be followed in accordance with the safety requirements outlined in Section 8.4.

### **8.1.10 Participant Blinding/Unblinding**

This is an open-label study; there is no blinding for this study.

### **8.1.11 Calibration of Equipment**

The investigator or qualified designee has the responsibility to ensure that any device or instrument used for a clinical evaluation/test during a clinical study that provides information about inclusion/exclusion criteria and/or safety or efficacy parameters shall be suitably calibrated and/or maintained to ensure that the data obtained are reliable and/or reproducible. Documentation of equipment calibration must be retained as source documentation at the study site.

## **8.2 Immunogenicity Assessments**

Sera from participants will be used to measure anti-HBs concentration using the hepatitis B ECi assay.

Blood collection, storage and shipment instructions for serum samples will be provided in the operations/laboratory manual.

### **8.2.1 Hepatitis B ECi Assay**

The purpose of the hepatitis B ECi assay is to detect total antibody to human plasma-derived HBsAg subtypes ad and ay before and after vaccination with HBsAg containing vaccine(s). This is the primary assay used to evaluate the serological response to the vaccine(s). The assay is a solid phase sandwich enzyme-labeled immunoassay. Results for the assay are reported in mIU/mL.

This assay involves the reaction of anti-HBs in a test sample with HBsAg (ad and ay subtypes) coated onto the wells. An HRP-labeled HBsAg conjugate (ad and ay subtypes) then formed a complex with the bound anti-HBs, forming an “antigen sandwich”. Unbound materials were removed by washing. A reagent that contained luminogenic substrates (a luminol derivative and a peracid salt) and an electron transfer agent was added to the wells. The HRP in the bound conjugate catalyzed the oxidation of the luminol derivative, producing light. The electron transfer agent increased the level and duration of the light produced. The amount of HRP conjugate bound and subsequent light produced was indicative of the concentration of anti-HBs present in the sample.

Three internally prepared control serum pools, consisting of a high-positive, low-positive, and negative control, were used to monitor the performance of the assay. These pools were each prepared from 4 individual human immune sera obtained from an external vendor. Additionally, there were anti-HBs positive and negative manufacturer-supplied controls, which were prepared from freeze-dried recalcified human plasma. The hepatitis B WHO International reference standard at 10 mIU/mL was also run as a control in every assay. The LLOQ of the assay is 5 mIU/mL.

## **8.3 Safety Assessments**

Details regarding specific safety procedures/assessments to be performed in this study are provided in this section.

Planned time points for all safety assessments are provided in the SoA.

### **8.3.1 Physical Examinations**

A targeted physical examination will be performed as indicated in Section 1.3. Any clinically significant abnormality will be recorded on the appropriate eCRF. The targeted physical examination procedure includes obtaining vital signs (heart rate, respiratory rate, and body temperature), auscultation of the heart and lung, and examination of the abdomen, further assessment if deemed necessary by the investigator or medically qualified designee.

Findings related to the physical examinations should be documented in the participant's chart/source documentation.

### **8.3.2 Body Temperature Measurement**

Pre-vaccination body temperature will be taken by study staff as indicated in Section 1.3. Participants who have febrile illness (defined as oral temperature  $\geq 38.1^{\circ}\text{C}$  [ $\geq 100.5^{\circ}\text{F}$ ] or axillary  $\geq 37.8^{\circ}\text{C}$  [ $\geq 100.0^{\circ}\text{F}$ ]) within 72 hours of vaccination must be rescheduled.

Oral is the preferred method of obtaining participant's temperature. If an axillary temperature is reported to be  $\geq 37.8^{\circ}\text{C}$  ( $\geq 100.0^{\circ}\text{F}$ ), an oral temperature must be taken. Temperature readings should be taken at approximately the same time each day. Use of temporal or tympanic thermometers to collect temperature for this study is prohibited.

### **8.3.3 Clinical Laboratory Assessments**

There are no laboratory safety evaluations required by the protocol.

## **8.4 Adverse Events, Serious Adverse Events, and Other Reportable Safety Events**

The definitions of an AE or SAE, as well as the method of recording, evaluating, and assessing causality of AE and SAE and the procedures for completing and transmitting AE, SAE, and other reportable safety event reports can be found in Appendix 3.

Adverse events, SAEs, and other reportable safety events will be reported by the participant (or, when appropriate, by a caregiver, surrogate, or the participant's legally authorized representative).

The investigator and any designees are responsible for detecting, documenting, and reporting events that meet the definition of a NSAE that leads to exclusion from study or results in discontinuation from study or SAE as well as other reportable safety events. Investigators remain responsible for following up NSAEs that lead to exclusion from study or result in discontinuation from study, SAEs, and other reportable safety events for outcome according to Section 8.4.3.

The investigator, who is a qualified physician, will assess events that meet the definition of a NSAE that leads to exclusion from study or results in discontinuation from study or SAE as well as other reportable safety events with respect to seriousness, intensity and causality.

#### 8.4.1 Time Period and Frequency for Collecting AE, SAE, and Other Reportable Safety Event Information

All AEs, SAEs, and other reportable safety events that occur after the consent form is signed but before allocation must be reported by the investigator if they cause the participant to be excluded from the study, or are the result of a protocol-specified intervention, including but not limited to washout or discontinuation of usual therapy, diet, placebo, or a procedure.

NSAEs that lead to exclusion from study or result in discontinuation from study, SAEs including death, and other reportable safety events must be reported by the investigator throughout the duration of the individual's participation in the study, regardless of whether or not related to the Sponsor's product.

Investigators are not obligated to actively seek NSAEs or SAEs or other reportable safety events in former study participants. However, if the investigator learns of any SAE, including a death, at any time after a participant has been discharged from the study, and he/she considers the event to be reasonably related to the study intervention or study participation, the investigator must promptly notify the Sponsor.

All initial and follow-up NSAEs that lead to exclusion from study or result in discontinuation from study, SAEs, and other reportable safety events will be recorded and reported to the Sponsor or designee within the time frames as indicated [Table 2](#).

Table 2 Reporting Time Periods and Time Frames for Adverse Events and Other Reportable Safety Events

Type of Event	Reporting Time Period: Consent to Randomization/ Allocation	Reporting Time Period: Randomization/ Allocation through Protocol-specified Follow-up Period	Reporting Time Period: After the Protocol-specified Follow-up Period	Time Frame to Report Event and Follow-up Information to Sponsor:
NSAE	Report if: - due to protocol-specified intervention - causes exclusion - participant is receiving placebo run-in or other run-in treatment	Report if: - led to discontinuation from study	Not required	Per data entry guidelines
SAE	Report if: - due to protocol-specified intervention - causes exclusion - participant is receiving placebo run-in or other run-in treatment	Report all	Report if: - drug/vaccine related. - any death until participant completion of study (Follow ongoing to outcome)	Within 24 hours of learning of event

Type of Event	Reporting Time Period: Consent to Randomization/Allocation	Reporting Time Period: Randomization/Allocation through Protocol-specified Follow-up Period	Reporting Time Period: After the Protocol-specified Follow-up Period	Time Frame to Report Event and Follow-up Information to Sponsor:
Pregnancy/ Lactation Exposure	Report if: - participant has been exposed to any protocol-specified intervention (eg, procedure, washout or run-in treatment including placebo run-in)	Report all	Previously reported – Follow to completion/termination; report outcome	Within 24 hours of learning of event
ECI (require regulatory reporting)	There are no events of clinical interest for this study.			
ECI (do not require regulatory reporting)	There are no events of clinical interest for this study.			
Cancer	Report if: - due to intervention - causes exclusion	Report all	Not required	Within 5 calendar days of learning of event (unless serious)
Overdose	Report if: - receiving placebo run-in or other run-in medication	Report all	Not required	Within 5 calendar days of learning of event

ECI=event of clinical interest; NSAE=nonserious adverse event; SAE=serious adverse event

#### 8.4.2 Method of Detecting AEs, SAEs, and Other Reportable Safety Events

Care will be taken not to introduce bias when detecting NSAEs that lead to exclusion from study or result in discontinuation from study and/or SAEs and other reportable safety events. Open-ended and nonleading verbal questioning of the participant is the preferred method to inquire about AE occurrence.

#### 8.4.3 Follow-up of AE, SAE, and Other Reportable Safety Event Information

After the initial NSAE that lead to exclusion from study or result in discontinuation from study /SAE report, the investigator is required to proactively follow each participant at subsequent visits/contacts. All SAEs, and other reportable safety events, including pregnancy and exposure during breastfeeding, cancer, and overdose will be followed until resolution, stabilization, until the event is otherwise explained, or the participant is lost to follow-up (as defined in Section 7.3). In addition, the investigator will make every attempt to follow all NSAEs that lead to exclusion from study or result in discontinuation from study that occur in

allocated participants for outcome. Further information on follow-up procedures is given in Appendix 3.

#### **8.4.4 Regulatory Reporting Requirements for SAE**

Prompt notification (within 24 hours) by the investigator to the Sponsor of SAE is essential so that legal obligations and ethical responsibilities towards the safety of participants and the safety of a study intervention under clinical investigation are met.

The Sponsor has a legal responsibility to notify both the local regulatory authority and other regulatory agencies about the safety of a study intervention under clinical investigation. The Sponsor will comply with country-specific regulatory requirements and global laws and regulations relating to safety reporting to regulatory authorities, IRB/IECs, and investigators.

Investigator safety reports must be prepared for SUSARs according to local regulatory requirements and Sponsor policy and forwarded to investigators as necessary.

An investigator who receives an investigator safety report describing an SAE or other specific safety information (eg, summary or listing of SAE) from the Sponsor will file it along with the IB and will notify the IRB/IEC, if appropriate according to local requirements.

#### **8.4.5 Pregnancy and Exposure During Breastfeeding**

Although pregnancy and infant exposure during breastfeeding are not considered AEs, any pregnancy or infant exposure during breastfeeding in a participant (spontaneously reported to the investigator or their designee) that occurs during the study are reportable to the Sponsor.

All reported pregnancies must be followed to the completion/termination of the pregnancy. Pregnancy outcomes of spontaneous abortion, missed abortion, benign hydatidiform mole, blighted ovum, fetal death, intrauterine death, miscarriage, and stillbirth must be reported as serious events (Important Medical Events). If the pregnancy continues to term, the outcome (health of infant) must also be reported.

#### **8.4.6 Disease-related Events and/or Disease-related Outcomes Not Qualifying as AEs or SAEs**

Not applicable

#### **8.4.7 Events of Clinical Interest**

#### **8.5 Treatment of Overdose**

In this study, an overdose is the administration of more than 1 dose of study vaccine.

No specific information is available on the treatment of overdose.

All reports of overdose must be reported by the investigator within 5 calendar days to the Sponsor either by electronic media or paper. Electronic reporting procedures can be found in

the EDC data entry guidelines. Paper reporting procedures can be found in the Investigator Trial File Binder (or equivalent).

## **8.6 Pharmacokinetics**

PK parameters will not be evaluated in this study.

## **8.7 Pharmacodynamics**

Pharmacodynamic parameters will not be evaluated in this study.

## **8.8 Biomarkers**

Biomarkers are not evaluated in this study.

## **8.9 Planned Genetic Analysis Sample Collection**

Planned genetic analysis samples will not be evaluated in this study.

## **8.10 Future Biomedical Research Sample Collection**

Not applicable

## **8.11 Medical Resource Utilization and Health Economics**

Medical Resource Utilization and Health Economics are not evaluated in this study.

## **8.12 Visit Requirements**

Visit requirements are outlined in Section 1.3. Specific procedure-related details are provided in Section 8.

### **8.12.1 Screening**

Screening procedures/eligibility criteria will be conducted at Visit 1 as outlined in Section 1.3. Screening procedures may be repeated after consultation with the Sponsor.

### **8.12.2 Treatment Period/Vaccination Visit**

Requirements during the treatment period are outlined in Section 1.3.

## **9 STATISTICAL ANALYSIS PLAN**

This section outlines the statistical analysis strategy and procedures for the study. Changes to analyses made after the protocol has been finalized will be documented in an sSAP and referenced in the CSR for the study. Post-hoc exploratory analyses will be clearly identified in the CSR.

## 9.1 Statistical Analysis Plan Summary

Key elements of the statistical analysis plan are summarized below; the comprehensive plan is provided in Sections 9.2 to 9.12.

Study Design Overview	A Hepatitis B Vaccine Challenge Study to Demonstrate the Durability of Protection Against Hepatitis B Virus Infection in Healthy Children Vaccinated Approximately 9 Years Previously With a 2- or 3-Dose Infant Series and Toddler Dose of Vaxelis®
Treatment Assignment	This is a single group, open-label, non-randomized study. Participants will receive a single-dose of HBVAXPRO™.
Analysis Populations	Immunogenicity: Per-Protocol (PP); Safety: All Participants as Treated (APaT)
Primary Endpoint	Immunogenicity: proportion of participants with a protective anti-HBs level of $\geq 10$ mIU/mL at 30 days post-challenge with HBVAXPRO™
Key Secondary Endpoint	Immunogenicity: anti-HBs GMCs pre-challenge on Day 1 and 30 days post-challenge with HBVAXPRO™
Statistical Methods for Key Immunogenicity Analyses	No statistical hypothesis testing will be performed for immunogenicity analyses in this study. For the immunogenicity endpoint, the point estimates and corresponding 95% CIs will be provided.
Statistical Methods for Key Safety Analyses	Any AEs resulting in discontinuation from study and SAEs will be reported and summarized descriptively.
Interim Analyses	No interim analyses are planned for this study.
Multiplicity	No statistical hypothesis testing will be performed for immunogenicity analyses in this study. Therefore, no adjustments for multiplicity are needed in this study.
Sample Size and Power	This is an estimation study. This study will enroll approximately 200 participants and will allow estimation of the primary immunogenicity endpoint with a 95% CI.

## 9.2 Responsibility for Analyses/In-house Blinding

The statistical analysis of the data obtained from this study will be the responsibility of the Clinical Biostatistics department of the Sponsor.

This study is being conducted as a non-randomized, open-label study, ie, participants, investigators, and Sponsor personnel will be aware of participant vaccination assignments after each participant is enrolled and vaccination is assigned.

The Clinical Biostatistics department will generate the allocation schedule(s) for study treatment assignment.

### **9.3 Hypotheses/Estimation**

Objectives of the study are stated in Section 3. This is an estimation study, and no formal hypothesis testing will be performed.

### **9.4 Analysis Endpoints**

Immunogenicity and safety endpoints that will be evaluated are listed below.

#### **9.4.1 Immunogenicity Endpoints**

The primary immunogenicity endpoint is the proportion of participants with a protective anti-HBs level of  $\geq 10$  mIU/mL at 30 days post-challenge with HBVAXPROTM, described in Section 3 and Section 4.2.1.1.

The secondary immunogenicity endpoint is the anti-HBs GMCs pre-challenge on Day 1 and 30 days post-challenge with HBVAXPROTM.

The exploratory immunogenicity endpoint includes the proportion of participants with a  $\geq 4$ -fold rise in anti-HBs level from pre-challenge on Day 1 to 30 days post-challenge with HBVAXPROTM.

#### **9.4.2 Safety Endpoints**

This study will monitor safety through the collection of AEs resulting in discontinuation from study and SAEs at Visit 1 and Visit 2 (Day 30).

### **9.5 Analysis Populations**

#### **9.5.1 Immunogenicity Analysis Populations**

The PP population will serve as the primary population for the analysis of immunogenicity data in this study. The PP population consists of all enrolled participants without deviations from the protocol that may substantially affect the results of the immunogenicity endpoint. Potential deviations that may result in the exclusion of a participant from the PP population for all immunogenicity analyses include:

- Failure to receive study vaccine at Visit 1 (Day 1)
- Receipt of a prohibited medication or prohibited vaccine prior to study vaccination
- Receipt of a prohibited medication or prohibited vaccine prior to blood sample collection at Visit 2 (Day 30)
- Collection of a blood sample at Visit 2 outside of the pre-specified analysis window (Day 23 to Day 44)

## **9.5.2 Safety Analysis Populations**

Safety summaries will be conducted in the APaT population, which consists of all participants who received study vaccine and had safety follow-up data after the vaccination.

## **9.6 Statistical Methods**

Statistical methods relating to immunogenicity analyses are described in Section 9.6.1. Statistical methods relating to safety analyses are described in Section 9.6.2.

### **9.6.1 Statistical Methods for Immunogenicity Analyses**

This section describes the statistical methods that address the immunogenicity objectives. No statistical hypothesis testing will be performed for immunogenicity analyses in this study. Point estimates and 95% CIs will be provided for both the primary and secondary immunogenicity objectives.

The point estimate for the primary immunogenicity objective will be calculated as the proportion of participants with a protective anti-HBs level of  $\geq 10$  mIU/mL at 30 days post-challenge with HBVAXPRO™. The CIs will be calculated based on the exact method proposed by Clopper and Pearson [Collett, D. 1999].

The point estimates for the secondary immunogenicity objective will be calculated by exponentiating the estimates of the mean of the natural log values. The 95% CIs will be derived by exponentiating the bounds of the CIs of the mean of the natural log values based on the t-distribution.

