## 2 INTRODUCTION

### 2.1 Study Rationale

The purpose of this study is to demonstrate the durability of protection against HBV infection approximately 9 years after vaccination with Vaxelis®. Vaxelis® (diphtheria, tetanus, pertussis [acellular, component], hepatitis B [rDNA], poliomyelitis [inactivated], and Haemophilus influenzae type b conjugate vaccine [adsorbed]) (DTaP5-HB-IPV-Hib) is a hexavalent vaccine indicated for active immunization to prevent the diseases caused by these pathogens. Vaxelis® was approved in the EU in 2016 and in the US in 2018. The hepatitis B component of the vaccine contains 10 µg of HBsAg produced by recombinant DNA technology and adsorbed on aluminum.

Hepatitis B vaccination results in increases in anti-HBs. Achievement of an anti-HBs concentration  $\geq 10$  mIU/mL 1 to 2 months after completion of a primary hepatitis B vaccination series is a globally accepted serologic correlate of protection against HBV infection [Plotkin, S. A. 2010] [World Health Organization 2017]. Anti-HBs levels wane over time and 15% to 50% of children who responded to the initial series will have low or undetectable levels 5 to 15 years later [Plotkin, S. A., et al 2008]. However, long-term protection is still expected due to the immune memory response [But, D. Y-K, et al 2008] [Bialek, S. R., et al 2008] [Roznovsky, L., et al 2010] [Su, F. H., et al 2007] [van der Sande, M. A. B., et al 2007] and additional doses of hepatitis B vaccine are not required or recommended [Schillie, S., et al 2018] [Leuridan, E. 2011] [FitzSimons, David, et al 2005] [European Consensus Group on Hepatitis B Immunity 2000].

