Consistent with other marketed hexavalent vaccines which include a hepatitis B component, the EMA requested a post-licensure study to assess the long-term persistence of anti-HBs 3 to 4 years after vaccination with Vaxelis® [European Medicines Agency 2013] [European Medicines Agency 2016]. The resultant study (V419-012) assessed children aged 4 to 5 years who received Vaxelis® or active comparator (Infanrix® hexa, GlaxoSmithKline Biologicals S.A, Rixensart, Belgium) in a 3 + 1 (Protocol V419-007: 3-dose primary series at 2, 3, and 4 months of age and a toddler dose at 12 months of age) or a 2 + 1 (Protocol V419-008: 2-dose primary series at 2 and 4 months of age and a toddler dose at 11 to 12 months of age) schedule. All of the children who participated in Study V419-012 had achieved an anti-HBs level of  $\geq 10$  mIU/mL after their vaccination series in V419-007 and V419-008 and were considered protected against HBV infection. The proportion of participants who had anti-HBs levels of  $\geq 10$  mIU/mL 3 to 4 years after the 3 + 1 schedule was 70.2% (95% CI: 63.1% to 76.6%) and 82.0% (95% CI: 75.8% to 87.2%) in Vaxelis® and Infanrix® hexa recipients, respectively. The proportion of participants who had anti-HBs levels of  $\geq 10$  mIU/mL 3 to 4 years after the 2+1 schedule was 65.8% (95% CI: 58.3% to 72.6%) and 83.7% (95% CI: 77.7% to 88.6%) in Vaxelis® and Infanrix® hexa recipients, respectively [CSR P012V419 2017].

Extended HBV protection after infant and toddler vaccinations has been documented with HBV-containing combination vaccines [Steiner, M., et al 2010] [Kosalaraksa, P., et al 2018] [Van Der Meeren, O., et al 2014] [Madhi, S. A., et al 2019]. Because the Phase 3 studies of

Vaxelis® (Protocols V419-007 and V419-008) were conducted approximately 9 years before the planned initiation of this protocol (V419-013), the Phase 3 cohort provides an excellent opportunity to assess long-term persistent protection against HBV infection specifically in Vaxelis® recipients.

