## **7.3 Lost to Follow-up**

If a participant fails to return to the clinic for a required study visit and/or if the site is unable to contact the participant, the following procedures are to be performed:

- The site must attempt to contact the participant and reschedule the missed visit. If the participant is contacted, the participant should be counseled on the importance of maintaining the protocol-specified visit schedule.

- The investigator or designee must make every effort to regain contact with the participant at each missed visit (eg, telephone calls and/or a certified letter to the participant's last known mailing address or locally equivalent methods). These contact attempts should be documented in the participant's medical record.
- Note: A participant is not considered lost to follow-up until the last scheduled visit for the individual participant. The missing data for the participant will be managed via the prespecified statistical data handling and analysis guidelines.

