#### **10.1.8 Data Quality Assurance**

All participant data relating to the study will be recorded on printed or electronic CRF unless transmitted to the Sponsor or designee electronically (eg, laboratory data). The investigator or qualified designee is responsible for verifying that data entries are accurate and correct by physically or electronically signing the CRF.

Detailed information regarding Data Management procedures for this protocol will be provided separately.

The investigator must maintain accurate documentation (source data) that supports the information entered in the CRF.

The investigator must permit study-related monitoring, audits, IRB/IEC review, and regulatory agency inspections and provide direct access to source data documents.

Study documentation will be promptly and fully disclosed to the Sponsor by the investigator upon request and also shall be made available at the study site upon request for inspection, copying, review, and audit at reasonable times by representatives of the Sponsor or any regulatory authorities. The investigator agrees to promptly take any reasonable steps that are requested by the Sponsor or any regulatory authorities as a result of an audit or inspection to cure deficiencies in the study documentation and worksheets/CRFs.

The Sponsor or designee is responsible for the data management of this study including quality checking of the data.

Study monitors will perform ongoing source data review and verification to confirm that data entered into the CRF by authorized site personnel are accurate, complete, and verifiable from source documents; that the safety and rights of participants are being protected; and that the

study is being conducted in accordance with the currently approved protocol and any other study agreements, ICH GCP, and all applicable regulatory requirements.

Records and documents, including signed ICF, pertaining to the conduct of this study must be retained by the investigator for 15 years after study completion unless local regulations or institutional policies require a longer retention period. No records may be destroyed during the retention period without the written approval of the Sponsor. No records may be transferred to another location or party without written notification to the Sponsor.

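### Does the lack of a stated rule for anti-HBs results below the 5 mIU/mL LLOQ undermine the Day 1 GMC and the 4-fold rise?

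*Combined protocol and SAP*

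**What the plan says.** Section 8.2.1 states: "The LLOQ of the assay is 5 mIU/mL". It does not say whether lower results come back as numbers or as below 5.

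Section 9.4.1 makes the Day 1 and Day 30 GMCs the secondary endpoint. The share of children with a 4-fold or greater "fold rise in anti-HBs level from pre-challenge on Day 1 to 30 days post-challenge" is exploratory. Section 9.6.1 has the GMC "calculated by exponentiating the estimates of the mean of the natural log values", with a t-based interval on the same scale. It covers the primary and secondary objectives only and gives no method for the fold rise. Section 9.10 repeats the primary and secondary estimates by prior schedule.

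Three places point to other material, and none is said to hold an LLOQ rule:

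- Section 7.3 says missing data after loss to follow-up will be "managed via the prespecified statistical data handling and analysis guidelines". A result below the LLOQ is not missing.
- Section 8.2: "Blood collection, storage and shipment instructions for serum samples will be provided in the operations/laboratory manual".
- Section 10.1.8: "Detailed information regarding Data Management procedures for this protocol will be provided separately".

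Section 9.1 presents Sections 9.2 to 9.12 as the full plan, and the opening of Section 9 reserves the supplemental SAP for later changes.

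**The concern.** A log mean needs a number for every child, and a fold rise needs a Day 1 denominator. Three readings are open for a result below 5: the value as reported, LLOQ/2 (2.5), or LLOQ (5). They give different answers, so two analysts could report different Day 1 GMCs from the same data.

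Such results are to be expected. Section 2.1 says that "15% to 50% of children who responded to the initial series will have low or undetectable levels 5 to 15 years later". It also says of the earlier persistence study: "All of the children who participated in Study V419-012 had achieved an anti-HBs level of" at least 10 mIU/mL after the series. Even so, only 70.2% (3 + 1) and 65.8% (2 + 1) of the Vaxelis recipients in it were still at or above 10 after 3 to 4 years. This study samples at about 9 years.

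At stake would be half of the key secondary endpoint, its split by schedule, and the only planned within-child measure of the rise. Because the study is open-label, the rule could in principle be settled after Day 1 results are known.

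**Working it through.** The plan gives no GMC, fold-rise or below-LLOQ figure to reproduce, so the check sizes the gap.

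**Inputs from the documents.** LLOQ 5 mIU/mL (8.2.1). About 200 children and 95% at or above 10 on Day 30 (9.9.1). Share at or above 10 at 3 to 4 years: 65.8% and 70.2% (2.1). Upper end of the waning range: 50% (2.1), reading low or undetectable as below 10, which is an assumption.

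**Other assumptions.** Lognormal titres with ln-scale SD 1.0 to 1.8 on Day 1. For the fold rise, Day 30 SD 1.5 or 2.0 and Day 1 to Day 30 correlation 0.3 or 0.7.

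**Step 1: effect on the Day 1 GMC.** Moving a share f of results from 2.5 to 5 adds f × (ln 5 − ln 2.5) = f × ln 2 to the mean ln value. So GMC(LLOQ) / GMC(LLOQ/2) = 2^f, whatever the distribution above 5.

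**Step 2: size of f.** If a share p is at or above 10, the ln-scale mean is μ = ln 10 + z_p × SD, and f = Φ(−ln 2 / SD − z_p).

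- p = 70.2% (z = 0.530), SD 1.0: f = Φ(−1.223) = 0.111, 2^f = 1.08.
- p = 65.8% (z = 0.407), SD 1.8: f = Φ(−0.792) = 0.214, 2^f = 1.16.
- p = 50% (z = 0), SD 1.0: f = Φ(−0.693) = 0.244, 2^f = 1.18.
- p = 50%, SD 1.8: f = Φ(−0.385) = 0.350, 2^f = 1.28.

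**Step 3: level of the GMC.** With a = (ln 5 − μ)/SD, the expected mean ln value under substitution c is μ(1 − f) + SD × φ(a) + f × ln c. At SD 1.5:

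| Share ≥10 | Model GMC | LLOQ/2 | LLOQ |
|---|---|---|---|
| 70.2% | 22.2 | 22.5 | 25.1 |
| 65.8% | 18.4 | 18.9 | 21.6 |
| 50% | 10.0 | 11.0 | 13.7 |

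**Step 4: interval behaviour** (4000 simulated trials per scenario, SD 1.0, 1.2, 1.5 and 1.8).

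| | 65.8–70.2% ≥10 | 50% ≥10 |
|---|---|---|
| 95% CI coverage, LLOQ/2, n = 200 | 91–95% | 61–95% |
| 95% CI coverage, LLOQ, n = 200 | 45–87% | 0–27% |
| LLOQ estimate outside the LLOQ/2 CI, n = 200 | at most about 0.1% | 90–96% |
| Same, n = 100 per schedule (assumed split) | 0% | roughly 7–17% |

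**Step 5: the 4-fold rise.** A child below 5 on Day 1 needs 4 × 2.5 = 10 on Day 30 under LLOQ/2, or 4 × 5 = 20 under LLOQ. Only children below 5 on Day 1 with a Day 30 value from 10 to under 20 change status. That is about 2 to 8 of 200 at 65.8–70.2% (1 to 4 percentage points), and about 4 to 11 of 200 at 50% (2 to 5 points). The modelled 4-fold rate at 65.8–70.2% is about 49% to 85%. The Clopper-Pearson half-width there is 7.1 points at 98/200 and 5.2 at 170/200. Table 3 is not the comparison to use, since it concerns the primary endpoint at 85% to 95% response.

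**Step 6: what cannot move much.** The primary cut-off of 10 is above 5, so a result below the LLOQ is a non-response under every reading. If 95% reach 10 on Day 30, at most 5% can be below 5, so the rule moves the Day 30 GMC by a factor of at most 2^0.05 = 1.035.

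**The case for a change.** The best case for a change is that no section supplies the rule, that the affected quantity is a named endpoint, and that the choice is not neutral. LLOQ substitution biases the GMC upward and covers poorly even at the documented rates (45% to 87%). Waning to year 9 could push the share below 5 above what was seen at 3 to 4 years. In the 50% scenario the two full-sample estimates usually disagree by more than the interval allows, and LLOQ/2 itself overstates the GMC when the spread is wide (12.0 against 10.0 at SD 1.8). One added sentence would cost almost nothing.

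Much of this stands as description. The omission is real and the arithmetic reproduces. It does not show that the plan is wrong, because the plan adopts neither rule. Analysts must assign some value to compute the mean at all. LLOQ/2 is a standard choice and does well at the only rates documented for this vaccine. The larger discrepancy needs n = 200 and an assumed 50% scenario built on a general waning range. At 100 per schedule in the same scenario it is roughly 7% to 17%.

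The worry about choosing the rule after seeing data carries little weight. There is one group, no comparator to favour and no hypothesis test. The opening of Section 9 also requires later analysis changes to be documented and post-hoc exploratory analyses to be identified, though that does not itself supply the rule. A second run at the LLOQ or an added median would be extra reporting and would correct no stated method.

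**Conclusion.** The concern does not call for a change. The plan leaves a routine data-handling detail unstated, one that analysts can fill with a standard substitution and name in the report.

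Between LLOQ/2 and LLOQ, the Day 1 GMC differs by 8% to 16% at the documented 65.8% to 70.2%, and by 18% to 28% if half the children are below 10. At the documented rates the 4-fold proportion moves by 1 to 4 points, inside a half-width of about 5 to 7. The primary endpoint does not move, the Day 30 GMC moves by at most about 3.5% under the planning response rate, and no decision rests on the Day 1 GMC or the exploratory rise.

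That the rule is missing, and the factor 2^f, are certain. The sizes rest on the assumed lognormal shape, SDs and correlations, and on a share below 5 that the documents do not give. If many more than a third of Day 1 results proved to be below 5, the Day 1 GMC would depend heavily on the rule used and should be read with that in mind. The conclusion on the primary objective would still stand.
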